6.3 Study Visits

The subsections that follow list the evaluations and procedures required at each study visit. Additionally, [Appendix 1](#) contains the schedules of events for each treatment group as a reference guide. To conserve space some visits are consolidated and some details omitted in the schedule of events. For complete details on individual study visit requirements, please refer to the procedures specified in each subsection.

6.3.1 Initial Escalation: Day 1 (Group 1)

The Initial Escalation Phase Visit for Group 1 subjects will occur within 10 days after the ARC003 Exit/ARC004 Screening and Baseline Visit. If the Initial Escalation is not started in this time frame, written approval to rescreen the subject and/or to waive any of the screening procedures must be obtained from the Sponsor's Medical Monitor.

A physician will be available at all times during the CRC peanut OIT dosing visits. Subjects must be free from active wheezing or a flare of atopic disease (eg, atopic dermatitis), or suspected intercurrent illness prior to initiating study product dose escalation. Additionally, subjects must be fully recovered (ie, back to their baseline state of health) from any preceding illness for \geq 3 to 7 days, depending on the investigator-determined severity of the illness.

The following assessments/procedures will be performed during the Initial Escalation Day 1 visit in the CRC:

- Concomitant medication update.

- Physical examination, including weight and height.
- Diet (food allergen exposure) history update.
- Pre-dose vital sign measurement (BP, PR, body temperature).
- Peak expiratory flow rate (PEFR), performed in all subjects 6 years of age or older, measured at approximately the same time for each assessment visit. Three attempts of PEFR should be performed, and the best attempt selected. For subjects 4 or 5 years of age: peak flow rates are to be attempted, but reliable performance is not required for the subject to enter the study or undergo study procedures at the investigating physician's discretion. The attempt must be documented, and a clinical assessment is required.
- Spirometry* (FEV₁), performed when PEFR shows a clinically relevant reduction or the subject shows clinical deterioration (e.g., active wheeze on physical examination); 3 attempts of FEV₁ should be performed, and the best attempt selected.

*Only for subjects 6 years of age and older who are able to adequately perform spirometry. In order to assess whether the subject is able to adequately perform spirometry, the spirometry must be attempted, and any attempt must be documented.

- Administration of AR101, with dosing beginning at 0.5 mg and progressing in graduated doses (if tolerated) of 1, 1.5, 3, and 6 mg. Following the first dose, subsequent doses will be delivered at 20 to 30 minute intervals. The schedule for initial day dose escalation is also shown in [Table 1](#).
- Post-dose vital sign measurements (BP, PR) within 15 to 30 minutes post-dose, and prior to next dose, and at 30-minute intervals thereafter, if the time between doses is extended, and for the duration of the post-dose observation period.
- Monitoring for AEs, including allergic symptoms (see below and [Section 6.5.3.1](#) and [Section 7.2](#)).
- Subjects will be reminded to continue to follow a peanut-avoidant diet for the duration of the study.

Subjects may have clear liquids or flavored gelatin (eg, Jell-O[®]) during the day of the initial day escalation procedure while they are being given the desensitization doses. At a minimum, subjects must be observed for 90 minutes (1½ hours) after completion of dose escalation, with vital sign measurements and assessment for signs and symptoms of allergic reaction performed every 30 minutes. Any signs or symptoms of allergic reaction will be recorded in the case report form (CRF) on the appropriate Dosing Symptom/AE form.

If Day 1 dose escalation is completed with no symptoms detected after 1½ hours of post-dose observation following the last dose, the subject may be sent home from the CRC. If the subject exhibited mild symptoms, the duration of the observation period should be a minimum of 1 hour after resolution of the symptoms. For moderate symptoms, the observation period should be extended to a minimum of 2 hours after resolution of the symptoms. And for severe symptoms, the subject should be observed for a minimum of 3 hours after resolution of the symptoms, either at the CRC or an emergency facility, as appropriate.

Any subject deemed to have severe symptoms that include hypoxia, hypotension, or change in mental status, stage 3 anaphylaxis defined in [Appendix 3](#), or who receives intensive therapy (to be determined by the investigator, but may include such interventions as IV epinephrine, intubation, or admission to an intensive care unit) for an allergic reaction at any time should be discussed with the Medical Monitor and discontinued from the study.

If dose-limiting symptoms occur at or before the 3-mg single dose, there will be no further dosing of study product, and the subject will be classified as an escalation failure and a nonresponder for the purpose of primary and key secondary analyses. The subject will be asked to return to the CRC 14 days following the last dose of study product to undergo an Early Discontinuation Visit ([Section 6.3.10](#)). Adverse events will be evaluated from the onset until the event is resolved or medically stable, or until 30 days after the Early Discontinuation Visit, whichever comes first.

If no dose-limiting symptoms occur during Day 1 dose escalation, or if dose-limiting symptoms occur only with the 6-mg single dose, the subject is to return to the CRC on the following day, Day 2, to confirm the tolerability of a single 3 mg dose of AR101.

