3.1.1 Initial Escalation (Group 1 Only)

All Initial Escalation doses will be administered by investigational site personnel under direct observation. Eligible subjects will initiate treatment with AR101 on Day 1, starting at a dose of 0.5 mg, increasing the dose at 20 to 30 minute intervals to a maximum dose of 6 mg ([Table 1](#)). Subjects who fail to tolerate ≥ 3 mg dose on Day 1 will be considered escalation failures and will be discontinued. Subjects who tolerate ≥ 3 mg dose on Day 1 will undergo confirmatory dosing of a single 3 mg dose on Day 2. Subjects who do not tolerate this confirmatory dose will be discontinued. Subjects who tolerate this confirmatory dose will enter the Up-dosing Period.

Table 1: Initial Escalation Schedule (Group 1 Subjects Only)

Initial Escalation Schedule (Group 1 only)		
Day 1 Dose Number	AR101 Dose, mg*	Cumulative AR101 Dose, mg
1	0.5	0.5
2	1	1.5
3	1.5	3
4	3	6
5	6	12
Day 2 Dose Number	AR101 Dose, mg	Cumulative AR101 Dose, mg
1	3	3

*All mg doses shown refer to milligrams of peanut protein.

Doses will be delivered at 20 to 30 minute intervals under direct observation.

Capsules are to be opened, contents sprinkled over an age-appropriate food, and mixed thoroughly.

Day 1: Subjects who are unable to tolerate a dose of 3 mg at the end of Day 1 will be considered escalation failures. Subjects who tolerate ≥ 3 mg on Day 1 will return on Day 2 to receive a 3-mg single dose.

Day 2: Subjects with either no symptoms or mild symptoms on Day 2 at 3 mg will start daily home dosing at 3 mg on Day 3.

Subjects with moderate or severe symptoms at 3 mg on either Day 1 or Day 2 will be considered escalation failures.

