6.3.2 Initial Escalation: Day 2 (Group 1)

On Day 2, the next consecutive day following Day 1, a single confirmatory 3-mg dose will be administered under medical supervision in the CRC. The only exception to Day 2 immediately following Day 1 is when unforeseen circumstances (eg, an intercurrent illness) creates a safety risk to provide the next dose, consistent with the rules for missed doses ([Section 6.6](#)).

Subjects must be free from active wheezing, a flare of atopic disease (eg, atopic dermatitis), or suspected intercurrent illness prior to continuing with Day 2 of the initial dose escalation.

The following assessments/procedures will be performed during the Initial Escalation Day 2 visit in the CRC:

- Concomitant medication update.
- Diet (food allergen exposure) history update.
- Symptom-directed physical examination.
- Pre-dose vital sign measurement (BP, PR, body temperature).
- Peak expiratory flow rate (PEFR), performed in all subjects 6 years of age or older, measured at approximately the same time for each assessment visit. Three attempts of PEFR should be performed, and the best attempt selected. For subjects 4 or 5 years of age: peak flow rates are to be attempted, but reliable performance is not required for the subject to enter the study or undergo study procedures at the investigating physician's discretion. The attempt must be documented, and a clinical assessment is required.
- Spirometry* (FEV₁), performed when PEFR shows a clinically relevant reduction or the subject shows clinical deterioration (e.g., active wheeze on physical examination); 3 attempts of FEV₁ should be performed, and the best attempt selected.

*Only for subjects 6 years of age and older who are able to adequately perform spirometry. In order to assess whether the subject is able to adequately perform spirometry, the spirometry must be attempted, and any attempt must be documented.

- Oral administration of a single 3 mg dose of AR101.
- Post-dose vital sign measurements (BP, PR) within 15 to 30 minutes post dose, prior to discharge, and as indicated per investigator discretion during the post-dose observation period. Subjects with moderate or severe symptoms should be monitored every 30 minutes.
- Monitoring for AEs, including allergic symptoms ([Section 7](#)).
- Diary review with subject.
- Subjects will be reminded to continue to follow a peanut-avoidant diet for the duration of the study.

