- In general, if a subject requires only 1 or 2 doses of an antihistamine to treat mild symptoms occurring during the course of the initial escalation, then the initial escalation may continue. If, however, the subject requires a second medication (eg, epinephrine or a beta-agonist) to treat the symptoms, or more than 2 doses of an antihistamine, the initial escalation is to be terminated and the subject is to receive no further OIT, even if the symptoms were assessed to be mild. Use of epinephrine to treat dose-related symptoms, even in the unlikely event that the symptoms are graded as mild, will be cause to terminate the initial escalation.
- **Moderate symptoms:** For *moderate symptoms*, if the symptoms are not worsening or amassing at a rapid pace, then a stepwise approach to treatment may be taken at the discretion of the investigator.
 - If the first action undertaken is to implement an observation period, the observation period should not exceed 30 minutes before either the symptoms are noted to be resolving or therapy is instituted.
 - Whether treatment is initiated immediately or after an observation period, the subject may be treated first with antihistamines or immediately with epinephrine, as deemed appropriate by the investigator.
 - Other therapies may be added either sequentially or simultaneously, per investigator judgment. If moderate symptoms occur at any of the doses below 6 mg (ie, up to and including 3 mg), then the desensitization procedure will be discontinued and the subject considered an escalation failure and desensitization nonresponder.
 - The decision to discontinue escalation is to be based solely on the determination of whether the allergic reaction was of moderate severity.
 - Although it is generally the case that some form of treatment will be instituted for moderate symptoms, treatment is not a requirement for assessing an allergic reaction as being of moderate severity.
- **Severe symptoms:** For *severe symptoms*, the actions taken should be to discontinue the initial escalation and administer the appropriate rescue medications. The desensitization procedure will be discontinued regardless of the dose at which the severe symptom or symptoms occurred, and the subject will be considered an escalation failure and desensitization nonresponder.

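### For a severe reaction only at the 6-mg Day 1 dose, Protocol 6.3.1 and Table 1 direct a 3-mg dose the next day, 6.5.4 ends dosing, and 4.3.1 gives a third rule

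*Protocol*

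**What the plan says.** Initial Escalation gives Group 1 subjects rising doses on Day 1, ending with 3 mg and then 6 mg, followed by a single 3-mg dose on Day 2.

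- **Section 6.3.1, Day 2 return.** The subject goes on to Day 2 if nothing dose-limiting happens, or "if dose-limiting symptoms occur only with the 6-mg single dose, the subject is to return to the CRC on the following day". No severity or treatment limit is attached.
- **Section 6.3.1, discontinuation.** Among severe reactions, the text discontinues a subset: "Any subject deemed to have severe symptoms that include hypoxia, hypotension, or change in mental status, stage 3 anaphylaxis", or intensive therapy. For severe symptoms in general it asks for at least 3 hours of observation after they resolve.
- **Section 3.1.1, Table 1.** Subjects who tolerate at least 3 mg "on Day 1 will return on Day 2 to receive a 3-mg single dose". The table note counts moderate or severe symptoms as failure at the 3-mg dose and does not mention 6 mg.
- **Section 6.5.4, severe symptoms.** "The desensitization procedure will be discontinued regardless of the dose at which the severe symptom or symptoms occurred", and the subject is an escalation failure and nonresponder.
- **Section 6.5.4, moderate symptoms.** The stop applies only at doses below 6 mg.
- **Section 6.5.4, mild symptoms.** If a second medication or more than 2 antihistamine doses are needed, "the initial escalation is to be terminated and the subject is to receive no further OIT". No exemption is given for 6 mg.
- **Section 4.3.1, item 2.** CoFAR Grade 3 symptoms terminate treatment. Subjects whose severe symptoms are not life-threatening, need no intensive therapy and carry no other sign of a serious condition may continue under close supervision if the investigator and Medical Monitor both agree.

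**The concern.** Take a subject who tolerates 3 mg and then, at 6 mg, has throat tightness with hoarseness or repetitive vomiting. Section 6.5.1 grades both as severe. One section orders a further dose the next day, another ends treatment, and a third makes continuing a joint decision. A site cannot follow all three. Section 6.3 refers sites to the visit subsections for complete visit requirements, so a site that acts on 6.3.1 is following the protocol.

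More than one supervised 3-mg dose is at stake. Under 6.3.2, a subject who tolerates Day 2 leaves with a 2-week supply and doses daily at home from Day 3. Table 2 then schedules 6 mg, the dose that caused the reaction. The study population starts at age 4 (Section 1.3).

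**Working it through.** There is no figure in the plan to reproduce. The check sets the rules side by side for a subject who tolerated 3 mg and reacted only at 6 mg on Day 1.

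| Reaction at 6 mg | 6.3.1 and Table 1 | 6.5.4 | Result |
|---|---|---|---|
| Severe, with a feature listed in 6.3.1 or intensive therapy | Discontinue under 6.3.1 | Discontinue | Agree |
| Severe, none of these | 3 mg on Day 2 | Discontinue; escalation failure and nonresponder | **Conflict** |
| Moderate | 3 mg on Day 2 | Stops only below 6 mg | Agree on severity alone |
| Mild, second medication or more than 2 antihistamine doses | 3 mg on Day 2 | No further OIT | **Conflict**, without the failure label |
| Mild, at most 2 antihistamine doses | 3 mg on Day 2 | May continue | Agree |

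**Can the second row be reconciled?**

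1. Section 6.5.4 cannot mean only that Day 1 escalation stops and the subject returns on Day 2, because it also labels the subject an escalation failure and nonresponder.
2. Section 6.5.4 exempts 6 mg from its moderate rule. For severe symptoms it says the dose does not matter, so no 6-mg exemption can be read in.
3. The discontinuation subset in 6.3.1 does not reach these cases. Appendix 3 places hoarseness and recurrent vomiting in stage 2, not stage 3.
4. The Day 2 entry check in 6.3.2 asks for no active wheezing, atopic flare or suspected intercurrent illness. A resolved, non-wheezing severe reaction passes it.
5. Section 4.3.1 item 2 matches neither rule. It is stricter than the unconditional return in 6.3.1 and looser than the unconditional stop in 6.5.4.

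**Size.** Section 1.4.1 expects severe symptoms in fewer than 1% of subjects at some point in dosing. Section 7.8.3 plans 130 Group 1 subjects. The ceiling is 0.01 × 130 = 1.3 subjects with severe symptoms over all doses and the whole course. The documents do not give the share that falls at the 6-mg Day 1 dose. They also do not give the number of mild reactions needing a second medication; 6.5.4 calls mild symptoms treated with epinephrine unlikely.

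**Effect on the analysis.** The primary endpoint is the frequency of treatment-related adverse events, and the 6-mg reaction counts whichever rule is followed. The SAP summarises challenge results in the Completer population (SAP Sections 4.2 and 9.1), which a subject stopped on Day 1 never enters. At most about one subject could be affected.

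**The case against.** The best case for leaving the text alone is that the protocol, read as a whole, already protects the subject. Section 6.5.4 is the section dedicated to acute reactions in Initial Escalation, and it stops severe cases. Section 4.3.1 makes termination the default for Grade 3 symptoms, and its item 8 requires termination if the investigator sees a safety threat. A Medical Monitor is available at all times. The Day 2 dose is supervised, half the reacting dose, and a level tolerated the day before. Section 6.3.2 is also less rigid than its opening suggests: "The only exception to Day 2 immediately following Day 1 is when unforeseen circumstances" continues by requiring that the circumstances create a safety risk, with intercurrent illness only as an example. A severe reaction the day before could reasonably qualify.

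Much of this stands, and it limits the harm. It does not say which instruction governs. The 6.3.2 clause only defers Day 2 and does not discontinue anyone. Section 6.3.1 is specific to the 6-mg dose and 6.5.4 is specific to severity, so neither clearly overrides the other. Figure 2, which shows the Day 1 algorithm, is not in the text available for this review. It might show sites which rule is meant, but it cannot remove the conflict between the written sections.

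Three stronger readings are tempting and are not supported:

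- **That 4.3.1 sides with 6.5.4, stops most of these subjects and needs no change.** Its joint-decision exception covers much the same ground as the case in dispute, so an unconditional stop written into 6.3.1 alone would leave a new conflict with 4.3.1.
- **That the frequency at the 6-mg Day 1 dose can be derived, for example by spreading severe reactions evenly over dose levels.** Nothing in the documents supports such a share.
- **That moderate 6-mg reactions given epinephrine are a further conflict between sections.** The moderate bullet says "The decision to discontinue escalation is to be based solely on the determination of whether the allergic reaction was of moderate severity", while the mild bullet treats epinephrine use as cause to terminate. The unclear point lies inside 6.5.4.

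**Conclusion.** The text is wrong as written for one defined case: severe symptoms only at the 6-mg Day 1 dose, without hypoxia, hypotension, mental-status change, stage 3 anaphylaxis or intensive therapy. Sections 6.3.1, 6.5.4 and 4.3.1 give three different instructions, and the most permissive leads to home dosing on Day 3. The severity is moderate because the rule concerns re-dosing after a severe allergic reaction, but the case is rare and the next dose is supervised.

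The size is at most 1.3 severe cases over the whole Group 1 course. This takes the planned 130 subjects and the protocol's own expectation of under 1%, which it draws from other OIT studies. The number at this one dose cannot be estimated. The effect on the analysis is negligible, and no bias in response rates should be inferred.

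The mild-symptom conflict is secondary. Stopping a mild 6-mg reaction for its treatment while moderate 6-mg reactions go on to Day 2 would be an odd ordering, so which rule should hold is for the sponsor to decide.

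**What to change.** 1. In Section 6.3.1, limit the Day 2 return. Suggested wording: *A subject whose dose-limiting symptoms arose only at 6 mg, and were not severe, comes back on Day 2. Severe symptoms at any Day 1 dose, 6 mg included, end dosing, and the subject counts as an escalation failure and nonresponder.*
2. Make the matching change in Section 3.1.1 and Table 1, and in the synopsis text and schedule for Initial Escalation.
3. State in Section 4.3.1 item 2 that the joint investigator and Medical Monitor exception does not apply during Initial Escalation.
4. Check that Figure 2 shows the same rule.
5. State which rule applies at 6 mg to mild symptoms needing a second medication or more than 2 antihistamine doses, and to moderate symptoms given epinephrine.

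If Group 1 Initial Escalation is already complete, the sponsor should identify any such subject and report which rule was applied.

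The cost is a few lines of protocol text and a site memo. There are no added visits, procedures or subjects. The severe-symptom stop is already in 6.5.4, and removing the 4.3.1 exception for this period brings that section into line with it. Extra stops for severe symptoms cannot exceed the 1.3-subject ceiling. Any stops under item 5 depend on the sponsor's choice and cannot be counted from the documents.

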6.3.2 Initial Escalation: Day 2 (Group 1)

On Day 2, the next consecutive day following Day 1, a single confirmatory 3-mg dose will be administered under medical supervision in the CRC. The only exception to Day 2 immediately following Day 1 is when unforeseen circumstances (eg, an intercurrent illness) creates a safety risk to provide the next dose, consistent with the rules for missed doses ([Section 6.6](#)).

Subjects must be free from active wheezing, a flare of atopic disease (eg, atopic dermatitis), or suspected intercurrent illness prior to continuing with Day 2 of the initial dose escalation.

The following assessments/procedures will be performed during the Initial Escalation Day 2 visit in the CRC:

- Concomitant medication update.
- Diet (food allergen exposure) history update.
- Symptom-directed physical examination.
- Pre-dose vital sign measurement (BP, PR, body temperature).
- Peak expiratory flow rate (PEFR), performed in all subjects 6 years of age or older, measured at approximately the same time for each assessment visit. Three attempts of PEFR should be performed, and the best attempt selected. For subjects 4 or 5 years of age: peak flow rates are to be attempted, but reliable performance is not required for the subject to enter the study or undergo study procedures at the investigating physician's discretion. The attempt must be documented, and a clinical assessment is required.
- Spirometry* (FEV₁), performed when PEFR shows a clinically relevant reduction or the subject shows clinical deterioration (e.g., active wheeze on physical examination); 3 attempts of FEV₁ should be performed, and the best attempt selected.

*Only for subjects 6 years of age and older who are able to adequately perform spirometry. In order to assess whether the subject is able to adequately perform spirometry, the spirometry must be attempted, and any attempt must be documented.

- Oral administration of a single 3 mg dose of AR101.
- Post-dose vital sign measurements (BP, PR) within 15 to 30 minutes post dose, prior to discharge, and as indicated per investigator discretion during the post-dose observation period. Subjects with moderate or severe symptoms should be monitored every 30 minutes.
- Monitoring for AEs, including allergic symptoms ([Section 7](#)).
- Diary review with subject.
- Subjects will be reminded to continue to follow a peanut-avoidant diet for the duration of the study.

At a minimum, subjects must be observed for 1½ hours after dose administration, with vital sign measurements and assessment for signs and symptoms of allergic reaction performed every 30 minutes. Any signs or symptoms of allergic reaction will be recorded in the CRF on the appropriate Dosing Symptom/AE form.

If Day 2 dosing is completed with no symptoms detected after 1½ hours of post-dose observation, the subject may be sent home from the CRC. If the subject exhibited mild symptoms, the duration of the observation period should be a minimum of 1 hour after resolution of the symptoms. For moderate symptoms, the observation period should be extended to a minimum of 2 hours after resolution of the symptoms. For severe symptoms, the subject should be observed for a minimum of 3 hours after resolution of the symptoms, either at the CRC or an emergency facility, as appropriate.

Any subject deemed to have severe symptoms that include hypoxia, hypotension, or change in mental status (stage 3 anaphylaxis defined in [Appendix 3](#)), or who receives intensive therapy (to be determined by the investigator, but may include such interventions as IV epinephrine, intubation, or admission to an intensive care unit) for an allergic reaction at any time should be discussed with the Medical Monitor and discontinued from the study.

If dose-limiting symptoms occur on Day 2, there will be no further dosing of AR101, and the subject will be classified as an escalation failure and a nonresponder for the purpose of primary and key secondary analyses. The subject will be asked to return to the CRC 14 days following the last dose of study product to undergo an Early Discontinuation Visit ([Section 6.3.10](#)). Adverse events will be evaluated from the onset until the event is resolved or medically stable, or until 30 days after the Early Discontinuation Visit, whichever comes first.

Those subjects who tolerate the single 3 mg dose of study product on Day 2 will be dispensed a 2-week supply of study product at the 3 mg/d dose level. They will be instructed to continue daily oral dosing at home, starting the following day (Study Day 3), and to continue daily home dosing at that dose level for 2 weeks until next escalation.

On Day 3, the site is to make telephone contact with the subject/subject's parent or guardian to enquire if any AEs (including allergic symptoms) occurred subsequent to the subject leaving the clinic, and to provide assistance in recording of, and responding to, any such events.

